6.2 Secondary Efficacy Analyses

6.2.1 Visual Acuity Defined as a Binary Outcome

A secondary analysis will be a treatment group comparison of the proportion of patients who have improved by 2 or more logMAR visual acuity lines 10 weeks after randomization for each treatment group, adjusted for baseline acuity scores using logistic regression.

6.2.2 Follow-up after the Primary Outcome

Patients in both groups who have improved by 1 or more lines from baseline to the 10-week outcome exam will continue in the study. Visits will occur every 10 ± 1 weeks until there is no improvement of one or more lines. A secondary analysis will be a treatment group comparison of the proportion of patients with at least two logMAR lines of visual acuity improvement between randomization and the visual acuity at the last study visit using logistic regression, adjusting for baseline visual acuity. An additional secondary analysis will be a treatment group comparison of logMAR visual acuity scores in the amblyopic eye at the last study visit, adjusted for baseline visual acuity scores in an analysis of covariance (ANCOVA) model.

6.2.3 Treatment Effect in Subgroups

The treatment effect in subgroups based on baseline factors will also be assessed in exploratory analyses. Interpretation of subgroup analyses will depend on whether the overall analysis demonstrates a significant treatment group difference. In the absence of an overall study difference, these subgroup analyses will be interpreted with caution.

669 The subgroups of interest are those based on visual acuity at the time of randomization, visual acuity at
670 the time of initial treatment, cause of amblyopia, length of prior treatment, maximum amount of prior
671 treatment (weekend vs daily), and age at randomization.

672

673 In accordance with NIH guidelines, a subgroup analysis of treatment effect according to gender, as
674 well as race/ethnicity, will be conducted. However, based on results from previous ATS studies, a
675 treatment effect by these variables is not expected.

676

677 The general approach for these exploratory analyses will be to repeat the primary analysis within each
678 subgroup.

679

680 **6.2.4 Stereoacuity**

681 Differences between treatment groups in stereoacuity measured at the 12-week off-atropine outcome
682 visit will be assessed using a comparison of the distributions with the exact Wilcoxon rank sum test.

683

684 **6.3 Primary Analysis for Safety**

685 **6.3.1 Sound Eye Acuity Data**

686 The loss of 2 or more lines in sound eye visual acuity from baseline to the 10-week masked exam will
687 be tabulated for each treatment group.

688

689 **6.3.2 Ocular Alignment**

690 Ocular alignment will be assessed at baseline and at 10 weeks after randomization. Development of a
691 new strabismus (no tropia at baseline and the presence of near and/or distance tropia at follow-up) or
692 an increase from baseline ≥ 10 PD will be tabulated by treatment group. Similarly, disappearance of a
693 heterotropia and a decrease in the angle of a preexisting strabismus by ≥ 10 PD will be tabulated.

694

695 **6.4 Sample Size**

696 We are unaware of any previous literature on the response to treatment of amblyopia still present after
697 initial treatment with weekend atropine. The sample size calculations were based on amblyopic eye
698 visual acuity data in a cohort of patients initially treated with weekend atropine from our previous
699 ATS4 and ATS8 studies.^{2,3} Patients in these studies were either randomized to weekend versus daily
700 atropine or weekend atropine versus weekend atropine with a plano lens over the sound eye for the
701 initial treatment of amblyopia. In ATS4, patients had office visits at 5 and 17 weeks following
702 randomization. In ATS8, patients had office visits at 5, 10, and 18 weeks following randomization.
703 Based on improvement in visual acuity among patients defined as stable, we assumed a standard
704 deviation for the change from baseline to 10-week outcome in this study of 0.14 logMAR. We will use
705 a two-sided alpha of 0.05, with 90% power to detect difference if the true difference in change from
706 baseline between groups is 0.075 logMAR at 10 weeks. With these assumptions, and accounting for
707 5% loss to follow-up, we have calculated a necessary total sample size of 158 patients.

708

709 A minimum of 158 patients are expected to be enrolled with a goal to enroll an appropriate
710 representation of minorities. As the enrollment goal approaches, sites will be notified of the end date
711 for recruitment. Patients who have signed an informed consent form can be randomized up until the
712 end date, which means the minimum recruitment goal might be exceeded. The maximum number of
713 randomized patients will be 178.

714

715 **6.5 Interim Analysis and Sample Size Re-estimation**

716 We are unaware of any previous literature reporting on the response to treatment of amblyopia still
717 present after initial treatment with weekend atropine. The sample size estimates above are based on a
718 study of the initial treatment of amblyopia and may not match our definition of no improvement in the
719 current study. Although we feel we have been conservative in our estimate of variation, a sample size
720 re-estimation will be performed once 50% of the originally planned number of patients have completed
721 the trial. A pooled estimate of variance without respect to treatment group will be calculated and used
722 to re-estimate sample size using a procedure that maintains masking.⁹ An adjustment will be made to
723 the final alpha based upon this interim sample size re-estimation.
724

Chapter 7: References

725
726
727
728
729
730
731
732
733
734
735
736
737
738
739
740
741
742
743
744
745
746

1. Pediatric Eye Disease Investigator Group. A randomized trial of atropine vs patching for treatment of moderate amblyopia in children. *Arch Ophthalmol* 2002;120:268-78.

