6.1 Primary Analysis for Efficacy

The study is evaluating 2 management approaches for amblyopia in patients already treated with weekend atropine:

1. Continued weekend atropine 1%
2. Intensified treatment: Weekend atropine 1% with plano lens

The primary analysis will be a treatment group comparison of logMAR visual acuity scores obtained 10 weeks after randomization, adjusted for baseline acuity scores in an analysis of covariance (ANCOVA) model.

The primary analysis will follow the intent-to-treat principle. Data will be included only from patients who complete the 10-week outcome. There will be no imputation of data for patients who are lost to follow-up or withdraw from the study prior to the 10-week outcome. In a secondary analysis, imputation methods for missing data will be assessed (such as last-observation-carried-forward and multiple imputation) for consistency with the primary analysis. A separate analysis also will be conducted including only patients whose outcome exams were performed within the time window for the visit.

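### Section 6.2.3 repeats the primary ANCOVA inside each subgroup and names no interaction test, so it gives no valid basis for saying that the effect differs between subgroup levels

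*Protocol*

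**What the plan says.** Section 6.2.3 (Treatment Effect in Subgroups) gives the analyses exploratory status: "The treatment effect in subgroups based on baseline factors will also be assessed in exploratory analyses". It lists six factors: acuity at randomization, acuity at initial treatment, cause of amblyopia, length of prior treatment, maximum prior treatment, and age. It adds gender and race/ethnicity to meet NIH guidelines, making eight, and remarks that no effect by these last two is expected.

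The method is: "The general approach for these exploratory analyses will be to repeat the primary analysis within each" subgroup. The analysis to be repeated is defined in Section 6.1: "The primary analysis will be a treatment group comparison of logMAR visual acuity scores obtained 10 weeks after randomization, adjusted for baseline acuity scores", by ANCOVA.

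On interpretation the section says: "Interpretation of subgroup analyses will depend on whether the overall analysis demonstrates a significant treatment group difference". The only instruction that follows is: "In the absence of an overall study difference, these subgroup analyses will be interpreted with caution". No treatment-by-factor interaction test, and no multiplicity rule for these analyses, appears anywhere in the protocol.

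**The concern.** The question behind a subgroup analysis is whether the treatment effect varies with the factor. Section 6.2.3 itself speaks of a treatment effect by gender and race/ethnicity, which is a question of effect modification. An ANCOVA run separately in each level answers something else, namely whether that level's effect is distinguishable from zero. A level can fail that test merely because it is small.

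The caution clause covers a null overall result. It says nothing about a positive one, which is when readers will most want to know who benefits. If significance in one level is then set against non-significance in another, the plano lens could be restricted or targeted by age, cause or acuity on no real evidence. The primary analysis, its alpha, the sample size and the safety analyses are not affected.

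**Working it through.** **Inputs.** From Section 6.4: difference 0.075 logMAR, SD of change 0.14, two-sided alpha 0.05, 90% power, 5% loss, total 158. From Section 1.3: 79 per group. The protocol gives no subgroup prevalences or cut-points, so the splits below are assumptions. The SD of change stands in for the ANCOVA residual SD. A smaller residual SD would act like a larger effect.

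**1. The plan's own figure.** A two-sample t-test with 75 per arm has 90.3% power. 2 × 75 / 0.95 = 157.9, so 158. The stated sample size reproduces.

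**2. Power in one half.** An equal split leaves 37.5 per arm in each level. SE = 0.14 × √(2/37.5) = 0.0323, and 0.075 / 0.0323 = 2.32. Power is 62.9% (t) or 64.0% (normal).

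**3. Discordance under a uniform effect.** With power p in both halves, P(exactly one significant) = 2p(1 − p).
- t: 2 × 0.629 × 0.371 = 0.467.
- Normal: 2 × 0.640 × 0.360 = 0.461.

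**4. Conditional on the overall result** (simulation, normal approximation, effect 0.075, equal halves). Discordance is 48% when the overall test is significant and 23% when it is not. The caution clause therefore covers the case with the lower figure.

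**5. Dependence on the true effect** (equal halves, same formula).

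| True uniform effect | Discordant (t) | Discordant (normal) |
|---|---|---|
| 0 | 9.5% | 9.5% |
| 0.0375 | 33% | 34% |
| 0.05 | 44% | 45% |
| 0.075 | 47% | 46% |
| 0.10 | 24% | 22% |

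**6. Dependence on split and size** (effect 0.075). For unequal levels the formula is p₁(1 − p₂) + p₂(1 − p₁).
- Splits with 75 per arm (normal): 60/40 gives 48%, 67/33 gives 51%, 75/25 gives 58%, 80/20 gives 63%.
- Equal halves (normal): 45% with 79 analysed per arm, and 41% with 89 per arm (the maximum of 178).
- Three equal levels of 25 per arm (cause of amblyopia has three categories in Section 2.2): power 45.9% each (t), so 1 − 0.459³ − 0.541³ = 0.745 are not all in agreement.

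**7. The alternative.** An interaction test at 5% declares a false difference in 5% of trials per factor, whatever the uniform effect and whether or not the overall result is significant. Its limits:
- SE of the difference between halves = 0.0323 × √2 = 0.0457. For a true difference of 0.075, 0.075 / 0.0457 = 1.64, giving power of about 37%. For 0.15 it is about 91%.
- Eight unadjusted tests, if independent: 1 − 0.95⁸ = 0.337.

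**The case against.** Several points on the other side have force.

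- **Chapter 6 is a synopsis.** It says that a final analysis plan will supersede it, and Section 6.2.3 speaks only of a general approach. Repeating the ANCOVA by level is an ordinary way to obtain subgroup estimates and does not exclude an interaction term. A reader might infer that the protocol considered an interaction test and rejected it; the text does not support that. What remains is that the protocol names a method, that the method does not compare levels, and that the chapter describes itself as the framework for the final plan.
- **No decision rule is stated.** A reader might infer that subgroup differences are to be judged by comparing significance between levels, and hence that spurious differences will arise about half the time. The protocol states no such rule, and an ANCOVA yields an estimate and interval as well as a p-value. This stands. Equally, the section offers no other basis for comparing levels.
- **The analyses are exploratory.** The section says so twice, and two of the eight factors are there to meet NIH guidelines. This limits the severity. It does not make the method suited to the question.
- **False positives under no effect.** A reader might add that many within-level tests will produce some significant results by chance when treatment does nothing. In that case the overall result is usually non-significant, and the protocol already asks for caution.
- **Interaction tests are weak here.** True, as shown in the working. That is a reason to report estimates with intervals and modest conclusions.

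**Conclusion.** The point holds in a conditional form. The protocol fixes a within-subgroup method for eight exploratory factors, names no test of whether the effect differs, and leaves a significant overall result without a caution. The figure of about 47% applies per two-level factor, and assumes a uniform effect equal to the planned 0.075, SD 0.14, about 75 analysed per arm and an equal split. It moves materially with the true effect and with the split, so it illustrates the problem and does not forecast this trial's results. Harm arises only if unequal significance is taken for unequal effect. The matter is worth correcting because the correction costs almost nothing. It does not threaten the primary conclusion.

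**What to change.** Amend Section 6.2.3, or carry the following into the final analysis plan:

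1. Any claim that the treatment effect differs by a baseline factor rests on a treatment-by-factor interaction term added to the primary ANCOVA, fitted to all patients in that analysis.
2. Within-level estimates with 95% confidence intervals are shown as description only, and a difference in significance between levels is not evidence of a difference in effect.
3. The exploratory caution applies whatever the overall result.
4. The limits are stated: about 37% power for a 0.075 logMAR difference between equal halves, and about a 34% chance of at least one false positive across eight unadjusted interaction tests if they are independent.

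The cost is wording only. No further data, visits or patients are needed. The price in inference is that most moderate differences between levels will go undetected, which the text should admit.
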